PK/Biomarkers (Central Laboratories):											
Serum for PK/Sarilumab Concentration 		X 	X 	X 	X	X	X	X 			X 
ADA		X				X 		X			X
Serum IL-6 		X		X	X	X	X	X			X
Serum sIL-6R 		X 						X			X
Blood for PCR SARS-CoV-2  (Not for determining the inclusion criteria)		X		X	X	X	X	X			X
Pharmacogenomics (optional genomic study):											
Blood for DNA/RNA 		X									

ESO: end of study, SpO2: oxygen saturation, CT-scan: computed tomography ECG: electrocardiogram, WOCBP: women of childbearing potential, PK: pharmacokinetic, ADA: antidrug antibodies, sIL-6R: soluble interleukin 6 receptor, IL: interleukin, PCR: polymerase chain reaction, SARS-CoV-2: Severe acute respiratory syndrome coronavirus 2, DNA: deoxyribonucleic acid, RNA: ribonucleic acid, SAE: serious adverse event, AESI: adverse event of special interest.

1. Laboratory-confirmed SARS-CoV-2 infection (eg by PCR), or other commercial or public health assay in any specimen within 2 weeks prior to randomization and no alternative explanation for current clinical condition is required for inclusion.
2. Screening and baseline may occur within 24 hours. Assessments that are noted for both visits should only be assessed once if the baseline visit is within 24 hours of the screening visit. All baseline samples, if obtained, should be collected before study drug administration at baseline visit except post-infusion PK and sIL-6R samples.
3. Patients will have an end of study (EOS) assessment to collect data on survival, adverse events, and history of hospital re-admission. This assessment may be performed by phone. This visit may be performed earlier if a patient withdraws from the study.
4. Patients discharged prior to Day 29 will have a follow-up phone call on Day 29 to collect data on all adverse events, and history of hospital re-admission.
5. Patients discharged prior to Day 29 should have a sample collected on or before day of discharge. Any sample collected within 24 hours of the day of discharge do not need to be repeated.

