2 STATISTICAL AND ANALYTICAL PROCEDURES

2.1 ANALYSIS ENDPOINTS

2.1.1 Demographic and baseline characteristics

In general, the baseline value is defined as the last available value prior to the first dose of investigational medicinal product (IMP) or the last available value on or before the date of randomization for patients who were randomized but never exposed to IMP, unless otherwise specified.

Demographic characteristics

The following demographic characteristics will be summarized separately by treatment and overall:

- Age at screening (years)
- Age group (≥ 18 and < 64 , ≥ 65 and < 84 , ≥ 85 years)
- Sex (Male, Female)
- Race (White, Black or African American, Asian, American Indian or Alaska Native, Native Hawaiian or Other Pacific Islander, Not Reported, Unknown). Note: Japanese will be included in Asian
- Ethnicity (Hispanic or Latino, Not Hispanic or Latino, Not Reported, Unknown)
- Baseline height (cm)
- Baseline weight (kg)
- Baseline weight category (< 50 , 50 to < 100 , ≥ 100 kg)
- Baseline body mass index (BMI, kg/m^2) (< 18.5 , 18.5 to < 25 , 25 to < 30 , ≥ 30)

Disease characteristics at baseline

The following baseline disease characteristics will be summarized:

- Severity of illness (per IRT) (Severe, Critical)
- Severity of illness (as recorded on CRFs) (Severe, Critical)
- Systemic corticosteroids use (per IRT) (Yes, No)
- Systemic corticosteroids use (as recorded on CRFs) (Yes, No)
- Clinical status using 7-point ordinal scale
- Body temperature prior to dosing ($^{\circ}\text{C}$) (defined as the highest temperature at any time prior to first dose)
- Fever (Yes, No)

- SARS-CoV-2 virus detected (Positive, Negative)
- CRP level

The other baseline disease characteristic includes

- Pneumonia status
 - Pneumonia present based on historical chest X-Ray, CT scan or MRI or lung auscultation (Yes, No)
 - Signs and symptoms: Fever, Cough, Dyspnea (Yes, No)
 - Time from dyspnea onset to baseline
 - Type of oxygen delivery device (Nasal cannula, simple face mask, non-rebreather face mask, high-flow nasal cannula, non-invasive ventilation, invasive mechanical ventilation, other)
 - Use of extracorporeal life support life support (Yes, No)
 - Use of renal replacement therapy (Yes, No)
 - Use of vasopressors (Yes, No)
- Oxygen administration and oxygenation
 - Supplemental Oxygen or mechanical ventilation used (Yes, No)
 - Oxygen flow rate (L/min)
 - Oxygen saturation (SpO₂ %) (range is 0% to 100%)

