2.4.4 Analyses of efficacy endpoints

Table 3 below summarizes the analyses for each type of efficacy endpoints in general.

Table 3 – Summary of analyses for each type of efficacy endpoint

Type of endpoint	Statistical method	Graphical presentation
Time-to-event	Log-rank test (stratified) Cox-PH model (stratified)	KM curve
% of patients over time	CMH test (stratified) Descriptive statistics	Bar plot over time
% of patients at end	CMH test (stratified) Descriptive statistics	Bar plot
Continuous variable over time	ANCOVA model Descriptive statistics	Line plot over time
Continuous variable at end	ANCOVA model Descriptive statistics	Histogram

For time to event analysis, the time to event duration is calculated as:

$$\text{Date of first occurrence/episode of the event} - \text{date of first dose} + 1.$$

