2.4.4.1 Analysis of primary efficacy endpoint(s)

The primary efficacy analysis will be pairwise comparisons between sarilumab doses (400 mg and 200 mg) and placebo with respect to the primary endpoint, time to improvement of 2 points in clinical status assessment from baseline using the 7-point ordinal scale, using a log-rank test stratified by randomization stratum with treatment as a fixed factor in the mITT population. P-values for the pairwise comparison of each sarilumab dose versus placebo will be provided.

Hazard ratios for the estimation of treatment effect of each sarilumab dose compared to placebo will be provided using Cox proportional hazards model stratified by the randomization stratum with treatment as a covariate, along with 2-sided confidence intervals. Kaplan-Meier (KM) plot and the median time-to-improvement of 2 points will also be provided by treatment groups.

Superiority of sarilumab over placebo will be declared if the null hypothesis is rejected at the 5% (2-sided) significance level following the multiplicity control procedure specified in [Section 2.4.4.3](#).

Patients who have an improvement of 2-points in clinical assessment or discharge (other than death) will be considered as events, while patients who do not experience improvement of 2-points will be censored at the last observation time point. Patients who take rescue medication in the study without improvement of 2-points before that will be censored at the date of rescue medication started.

In addition, the proportion of patients with at least 2-point improvement from baseline at each day post-baseline will be provided using descriptive statistics. Graphical presentations (bar charts) will be used to examine trends over time.

The analyses using the log-rank test and Cox PH model specified above will be repeated for the severe patients and critical patients at baseline as recorded on CRFs.

Baseline clinical status is defined as the worse (lower) value of screening visit and Day 1 prior to dosing. If there is a tie, flag Day 1 as baseline. Baseline values are 2, 3, 4, 5, or 6. Values 1 and 7 do not apply (if 1 or 7 appear, then data query is needed.)

Post-baseline clinical status values range from 1 through 7 on ordinal scale and data will be as recorded on the ordinal scale eCRF.

Handling of death or discharge on clinical status assessment (post-baseline)

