For patients who die, the clinical status recorded on the day of death will be replaced with “1=Death” and this value will be carried forward for all subsequent study days until end of study (Day 60). Death date may be obtained from Adverse Events or Disposition CRFs or phone call at Day 60 (end of study).

For patients who discharge early (other than death), the clinical status recorded on the earliest hospital discharge date will be replaced with 7 (not hospitalized), and this value will be carried forward for all subsequent study days until end of study (Day 60). Hospital discharge information (discharge date and discharge reason) may be obtained from the Discharge Reason eCRF. If there is subsequent hospitalization, the clinical status will not be replaced by 7 after the second hospitalization.

Handling of missing data on clinical status assessment (post-baseline)

For patients who are alive and not discharged (ie, still hospitalized), missing clinical status value (ordinal scale) on a given study day will be imputed using data on the type of oxygen delivery device used by the patient on that day (last type of device used if multiple types were used in a day).

Clinical status = 2 (if using invasive mechanical ventilation or ECMO), or
= 3 (if using non-invasive mechanical ventilation or high-flow nasal cannula), or
= 4 (if using nasal cannula, simple face mask, or non-rebreather face mask) or
= 5 (if not using supplemental oxygen)

Sensitivity analysis

The PPS and ITT will be used for sensitivity analysis of the primary efficacy endpoint, as described above.

Subgroup analyses

Descriptive analyses will be performed on the primary endpoint to summarize the treatment effect of each sarilumab dose versus placebo by the following variables:

- Age (<median, >=median)
- Age group (≥ 18 and < 64 , ≥ 65 and < 84 , ≥ 85 years)
- Sex (Male, Female)
- Race (White, Black or African American, Asian, Other). Note: Japanese will be grouped with Asian, a group with less than 5 patients in any treatment may be grouped with 'Other'
- Ethnicity (Hispanic or Latino, Not Hispanic or Latino)
- Severity of illness (per IRT) (Severe, Critical)
- Severity of illness (as recorded on CRFs) (Severe, Critical)
- Systemic corticosteroids use (per IRT) (Yes, No)
- Systemic corticosteroids use (as recorded on CRFs) (Yes, No)
- Fever status at baseline (Yes, No)
- Pneumonia present based on historical chest X-Ray, CT scan or MRI or lung auscultation (Yes, No)

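### The primary endpoint takes the worse of the screening and Day 1 scores as baseline, so improvement before dosing can count toward the 2-point response in both arms

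*SAP*

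**What the plan says.** For the 7-point scale, SAP section 2.4.4.1 says: "Baseline clinical status is defined as the worse (lower) value of screening visit and Day 1 prior to dosing". It adds that "Baseline values are 2, 3, 4, 5, or 6", and it has a rule for ties, so it expects some patients to have two pre-dose scores.

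The event rule in the same section is: "Patients who have an improvement of 2-points in clinical assessment or discharge (other than death) will be considered as events". SAP section 2.4.4 counts time from the first dose to the "Date of first occurrence/episode of the event". Neither passage requires the patient to be better than the last score before dosing.

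The general rule in SAP section 2.1.1 differs: "the baseline value is defined as the last available value prior to the first dose of investigational medicinal product (IMP". That section opens with a general qualifier and allows exceptions. The SpO2/FiO2 baseline in SAP section 2.4.4.2 follows the last-value rule. Protocol section 9.4.2 refers only to change from baseline and does not define baseline for this scale.

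Protocol section 1.3 places screening on Day -1 or Day 1. Its footnote 2 says "Screening and baseline may occur within 24 hours", and that assessments listed for both visits "should only be assessed once if the baseline visit is within 24 hours of the screening visit".

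The sensitivity analyses named for the primary endpoint use the per-protocol and ITT populations. Neither changes the baseline.

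**The concern.** The primary endpoint should measure change after randomized treatment. With the worse of two pre-dose scores as the reference, part of the 2-point improvement, or all of it, can lie before the first dose. Such a patient can become an event on the first post-dose assessment with no change since treatment began.

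Three things would be affected: the hazard ratio, the response rates by day, and the median time to improvement. The same baseline also enters secondary endpoints #1 (1-point improvement) and #2 (mean change on the scale). Because both planned sensitivity analyses keep the rule, neither would show how much of the result depends on it.

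**Working it through.** **1. What the rule does to individual patients.** The score needed is the baseline plus 2. Live discharge is an event under either rule.

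| Screening | Day 1 pre-dose | SAP baseline | Score needed (SAP) | Score needed (last pre-dose baseline) |
|---|---|---|---|---|
| 2 | 4 | 2 | 4, already met | 6 |
| 3 | 5 | 3 | 5, already met | 7 |
| 3 | 4 | 3 | 5, one more point | 6 |
| 4 | 3 | 3 | 5 | 5 |

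The first two rows are automatic events. The third has a lower threshold. In the fourth row the patient worsened before dosing and the two rules agree.

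**2. The plan's own power.** Inputs from SAP section 1.3: 160 versus 80 patients, 70% versus 45% improved at Day 15, two-sided 0.05, log-rank test, power of at least 90%.

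- With exponential times, HR = ln(0.30)/ln(0.55) = 2.01.
- Events by Day 15: 80 × 0.45 + 160 × 0.70 = 148.
- Schoenfeld power = Φ(√(148 × 1/3 × 2/3) × ln 2.01 − 1.96) = 98.0%. Freedman's formula gives 93.4%.
- With 199 events by Day 29, the two formulas give 99.7% and 98.0%.

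The stated lower bound of 90% is reproduced.

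**3. Effect of full pre-dose credit.** Let f be the share of patients who already meet the full 2 points before dosing. The documents do not give f, so it is an assumption, shown from 0 to 20%. The Day 15 rate becomes p(1 − f) + f, and the 25-point difference becomes 25(1 − f). At f = 10%, for example, 0.45 × 0.90 + 0.10 = 50.5% and 0.70 × 0.90 + 0.10 = 73.0%, a difference of 22.5 points. In numbers, f = 10% means 8 of 80 placebo and 16 of 160 sarilumab patients.

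Hazard ratio, power and type I error come from a simulated daily log-rank test: 80 versus 160 patients, censoring at Day 29, unstratified, 3,000 runs per setting. Patients in the share f have their event on Day 1 in both arms. The hazard ratio is a one-step log-rank estimate, so it starts at 1.95 and not at 2.01.

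| f | Day 15 rates | Difference (points) | HR | Power, planned effect | Power, 45% vs 63% | Type I error |
|---|---|---|---|---|---|---|
| 0 | 45.0% vs 70.0% | 25.0 | 1.95 | 99.6% | 90.3% | 4.5% |
| 2% | 46.1% vs 70.6% | 24.5 | 1.92 | 99.3% | not run | not run |
| 5% | 47.8% vs 71.5% | 23.8 | 1.89 | 99.2% | 85.9% | 5.0% |
| 10% | 50.5% vs 73.0% | 22.5 | 1.82 | 98.4% | 82.7% | 5.2% |
| 20% | 56.0% vs 76.0% | 20.0 | 1.74 | 95.0% | 73.5% | 4.5% |

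The 45% versus 63% column is an assumed smaller effect, chosen to start near 90% power. It is not in the plan.

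**4. Effect of 1-point credit.** These patients are not automatic events and must not be counted in f. If they are given twice the event hazard in both arms (an assumption), a 10% share gives HR 1.93 and a 20% share gives HR 1.91, both with power of 99.5%.

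**The case against.** The strongest case for leaving the rule alone has four parts.

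- **It is explicit and permitted.** SAP section 2.1.1 allows exceptions, so a reader who infers an internal contradiction goes too far. Nor is this scale the only one with a worst-value baseline: baseline temperature is the highest value before dosing. This stands. The temperature parallel is incomplete, though, because post-baseline temperature is also the highest of each day. The ordinal scale compares the worse of two readings with the score recorded for the day.
- **Few patients can be affected.** Footnote 2 of Protocol section 1.3 largely limits two scores to visits more than 24 hours apart, in a window that opens on Day -1. A 2-point gain in that time is probably rarer than a 1-point gain. This stands, and f cannot be pinned down from the documents.
- **The error is conservative.** A reader might infer a bias toward sarilumab or a risk of a false positive. The documents do not support that. The credit arises before dosing under randomization, and simulated type I error stays near 5%. Nor is the sample size undermined, since power at the planned effect is 95.0% even at f = 20%.
- **Changing it now has a price.** Protocol section 4.3 records that sponsor senior management has reviewed an unblinded interim report. SAP section 3 lists time to 2-point improvement in that analysis, and Protocol section 9.4 required the SAP to be final beforehand. This stands and shapes the fix.

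Two further inferences should be resisted. Pre-dose worsening is not treated unfairly, because the worse value is then the Day 1 value. The rule for missing post-baseline days, which takes the "last type of device used if multiple types were used in a day", is a separate matter. It gives no pre-dose credit and is no reason for a change here.

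**Conclusion.** The point holds as a weakness in the endpoint definition. The baseline rule credits pre-dose improvement to the post-dose period, fully for a 2-point gain and partly for a 1-point gain. No reason is stated, and no planned analysis would reveal it.

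The consequence is dilution: higher response rates and shorter times in both arms, and a hazard ratio nearer 1. At f = 5% the hazard ratio falls by 0.06 and the Day 15 difference by about 1.2 points. At f = 10% the falls are 0.13 and 2.5 points. The loss of power is small at the planned effect and would matter only if the true effect were clearly smaller, as in the 45% versus 63% case.

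These sizes rest on an assumed f, exponential times, an unstratified test, and no allowance for deaths or rescue medication.

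**What to change.** In SAP section 2.4.4.1, define baseline clinical status as the last 7-point score recorded before the first dose, using the screening score only when no Day 1 pre-dose score exists. Apply it to the primary endpoint and to secondary endpoints #1 and #2. The blinded team should make the change and document its date and reason before the primary database lock.

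If the sponsor prefers to keep the current rule because senior management has seen unblinded interim results on this endpoint, two additions are enough:

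- a pre-specified sensitivity analysis of the primary endpoint with the last pre-dose score as baseline;
- a count, by arm, of patients whose Day 1 pre-dose score was better than their screening score.

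Either route needs one or two sentences in the SAP and one extra derivation, with no new data. Replacing the rule would give slightly fewer or later primary events in both arms, and would change a primary-endpoint definition after the interim analysis, which is why authorship and timing must be on record. The sensitivity route avoids that but leaves any dilution in the primary test.

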Patients will be assessed daily while hospitalized. Discharged patients will be contacted by telephone on Day 29 to assess status and occurrence of re-admission to a hospital. Patients will undergo a series of efficacy, safety and laboratory assessments while in the hospital. Serum IL-6 and other markers will be collected and analyzed in a central laboratory. Nasopharyngeal (NP) samples to monitor viral infection and blood samples will be requested on day 1 (pre-dose), 4, 7, 15, 29 (or up until the day of discharge if the patient is discharged from the hospital before day 29).

Randomization will be stratified by:

- Severity of illness
  - Severe disease
  - Critical disease
- Systemic corticosteroids (Yes/No)

The severity categories are:

- Severe disease:
  - Requires supplemental oxygen administration by nasal cannula, simple face mask, or other similar oxygen delivery device
- Critical disease:
  - Requires supplemental oxygen requiring delivered by non-rebreather mask or high-flow nasal cannula
  - OR Use of invasive or non-invasive ventilation,
  - OR Requiring treatment in an intensive care unit.

Note: Participants meeting criteria for both severity categories will be stratified according to the more severe category.

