### Study Level Stopping Rules

An independent data monitoring committee (IDMC) will actively monitor the ongoing safety of patients and can make recommendations about early study closure or changes to the conduct of the study. The Sponsor may decide to stop or make changes to the study based on the recommendations of the IDMC.

A treatment arm may be discontinued if there is a clinically meaningful imbalance between treatment arms in any of the following safety criteria:

1. Incidence of SAEs
2. Incidence of AESIs
3. Progression of COVID-19 to more severe, critical or multi-organ dysfunction
4. Incidence of clinically significant recurrence of severe or critical disease after clinical improvement

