### 9.2 SAMPLE SIZE DETERMINATION

The sample size calculations are performed based on the primary endpoint, the time to improvement of 2 points in clinical status assessment from baseline using the 7-point ordinal scale.

Assuming that accrual duration is 3 months (~90 days) with each patient followed for a period of at least 29 days, the proportions of patients with two points improvement from baseline in clinical status assessment at day 15 are 45% and 70% for placebo and sarilumab, respectively, a total sample size of approximately 400 patients with a 2:2:1 randomization ratio provides at least 90% power for pairwise comparisons between each sarilumab dose (400 mg IV or 200 mg IV; n~160 each) and placebo (n~80), using a log-rank test of superiority at a two-sided significance level of 0.05. Sample size calculation was performed using PASS 14.

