2.5.3 Missing data

For categorical variables, patients with missing data are not included in calculations of percentages unless otherwise specified. When relevant, the number of patients with missing data is presented.

Handling of medication missing/partial dates

No imputation of medication start/end dates or times will be performed. If a medication date or time is missing or partially missing and it cannot be determined whether it was taken prior or concomitantly, it will be considered a prior, concomitant, and posttreatment medication.

Handling of adverse events with missing or partial date/time of onset

Missing or partial adverse event onset dates and times will be imputed so that if the partial adverse event onset date/time information does not indicate that the adverse event started prior to treatment or after the treatment-emergent adverse event period, the adverse event will be classified as treatment-emergent. No imputation of adverse event end dates/times will be performed. These data imputations are for categorization purpose only and will not be used in listings. No imputation is planned for date/time of adverse event resolution.

Handling of adverse events when date and time of first investigational medicinal product administration is missing

When the date and time of the first IMP administration is missing, all adverse events that occurred on or after the day of randomization should be considered as treatment-emergent adverse events. The exposure duration should be kept as missing.

The last dose intake should be clearly identified in the case report form and should not be approximated by the last returned package date.

Handling of missing assessment of relationship of adverse events to investigational medicinal product

If the assessment of the relationship to IMP is missing, then the relationship to IMP has to be assumed and the adverse event considered as such in the frequency tables of possibly related adverse events, but no imputation should be done at the data level.

Handling of missing severity of adverse events

If the severity is missing for one of the treatment-emergent occurrences of an AE, the maximal severity on the remaining occurrences will be considered. If the severity is missing for all the occurrences a “missing” category will be added in summary table.

Handling of potentially clinically significant abnormalities

If a patient has a missing baseline he will be grouped in the category “normal/missing at baseline.”

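### No planned analysis tests whether the primary improvement lasts, and the SAP gives a readmitted patient no ordinal score

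*SAP*

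**What the plan says.** **Primary event.** SAP 2.4.4 times every time-to-event endpoint from "Date of first occurrence/episode of the event". SAP 2.4.4.1 counts a 2-point improvement or a live discharge as the event and sets no minimum duration. The sensitivity analyses listed there repeat the analysis in the per-protocol and ITT populations.

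**Score after discharge.** SAP 2.4.4.1 sets the score to 7 on the first discharge date and carries it to every later study day up to Day 60. It then adds: "If there is subsequent hospitalization, the clinical status will not be replaced by 7 after the second hospitalization". No other value is named.

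**Data available after discharge.** The Schedule of Activities (Protocol 1.3) schedules the ordinal scale daily until discharge. Protocol 4.1 says: "Discharged patients will be contacted by telephone on Day 29 to assess status and occurrence of re-admission to a hospital". Footnote 4 of the Schedule lists the content of that call as adverse events and readmission history, with no ordinal score and no oxygen device.

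**Missing values.** SAP 2.4.4.1 imputes a missing score from that day's oxygen device for patients who are alive and not discharged, glossed as still in hospital. SAP 2.5.3 says: "For categorical variables, patients with missing data are not included in calculations of percentages unless otherwise specified".

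**Relapse as a monitored outcome.** Protocol 7.2 (Study Level Stopping Rules) and 9.6 list this among the safety criteria for discontinuing an arm: "Incidence of clinically significant recurrence of severe or critical disease after clinical improvement".

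**The concern.** There are two separate gaps.

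First, a patient at score 3 who is scored 5 on one day and intubated the next is a primary success. Other recovery endpoints in SAP 2.1.3.2 do require persistence: 48 hours for fever and oxygenation, 24 hours for NEWS2. If one arm had more short-lived improvement, the hazard ratio would not show it, and neither sensitivity analysis would reveal that the result depends on it.

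Second, a readmitted patient has no defined score. If the value is treated as missing, the patient leaves the percentages for endpoint #1 (tested by CMH at Days 4, 7, 15, 21 and 29) and for the daily 2-point proportions, and drops out of the endpoint #2 ANCOVA. A poor outcome would then be removed from the comparison instead of counted in it.

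**Working it through.** **1. What the SAP rules give for a readmitted patient.** Three readings are open.
- *Missing.* The 7 is withheld, no score is scheduled after the first discharge, the Day 29 call collects none, and SAP 2.5.3 removes the patient from the percentage. This is the most direct reading of the scheduled data.
- *Still 7.* This applies if the wording on the second hospitalization means after its end, so that the carry-forward still covers the readmission itself. A relapse then counts as improved.
- *Recorded or device-based score.* This applies if the site enters data during the readmission and the patient is read as still in hospital. If an absent device record were read as no oxygen, the score would be 5, an improvement from baseline 3 or 4.

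**2. The plan's own figure (Protocol 9.2).** Inputs: "proportions of patients with two points improvement from baseline in clinical status assessment at day 15 are 45% and 70% for placebo and sarilumab"; "each sarilumab dose (400 mg IV or 200 mg IV; n~160 each) and placebo (n~80"; and "using a log-rank test of superiority at a two-sided significance level of 0.05".
- Hazard ratio under exponential times = ln(0.30)/ln(0.55) = 2.01.
- Events by Day 15 = 80 × 0.45 + 160 × 0.70 = 36 + 112 = 148.
- Schoenfeld power = Φ(√(148 × 1/3 × 2/3) × ln 2.014 − 1.96) = Φ(2.05) = 98.0%.

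The stated power of at least 90% is met, so the sample size is not in question.

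**3. What a sustained event could change (relapse shares are assumptions).** Let a share q of improvers relapse and lose the event, so each Day 15 rate becomes p(1 − q). Recompute the hazard ratio, events and power as in step 2.

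| Relapse among improvers, placebo / sarilumab | Day 15 rates | HR | Events | Power |
|---|---|---|---|---|
| 0 / 0 | 45.0% / 70.0% | 2.01 | 148.0 | 98.0% |
| 5% / 5% | 42.75% / 66.5% | 1.96 | 140.6 | 96.4% |
| 10% / 10% | 40.5% / 63.0% | 1.92 | 133.2 | 94.2% |
| 20% / 20% | 36.0% / 56.0% | 1.84 | 118.4 | 87.8% |
| 5% / 10% | 42.75% / 63.0% | 1.78 | 135.0 | 88.6% |
| 10% / 20% | 40.5% / 56.0% | 1.58 | 122.0 | 66.5% |

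Equal relapse costs little until it is common. Unequal relapse changes the effect itself.

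**4. Dropping readmitted patients (readmission shares are assumptions).** Let p and s be the placebo and sarilumab shares improved before any readmission, and m the share readmitted, all previously improved. Counted as not improved, a rate is p − m; dropped, it is (p − m)/(1 − m). With equal m in both arms the dropped difference is (s − p)/(1 − m): the true difference is stretched by 1/(1 − m), and a true difference of zero stays zero.

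Daily 2-point proportion at the planning rates, difference in points:

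| Readmitted, placebo / sarilumab | Dropped | Counted as not improved |
|---|---|---|
| 2% / 2% | 25.5 | 25.0 |
| 5% / 5% | 26.3 | 25.0 |
| 10% / 10% | 27.8 | 25.0 |
| 5% / 10% | 24.6 | 20.0 |
| 2% / 10% | 22.8 | 17.0 |

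Endpoint #1 with a smaller assumed effect, readmitted patients taken as truly not improved: 120/160 − 56/80 = 75.0% − 70.0% = 5.0 points.
- Equal 5% readmission (8 and 4 dropped): 120/152 − 56/76 = 78.9% − 73.7% = 5.3 points. Each rate is overstated by about 4 points.
- 10% against 4% (16 and 3 dropped): 120/144 − 56/77 = 83.3% − 72.7% = 10.6 points.

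**The case against.** **Relapse is not invisible.** A reader might infer from the first-occurrence rule that the trial cannot see relapse. The documents do not support that. The patient intubated the day after a score of 5 is scored 2 in the daily 7-category summaries and the daily 2-point proportions, and on the scheduled days in endpoints #1 and #2. Death is set to 1 and carried forward, and it counts in the key secondary endpoint. Ventilator-free credit after early discharge runs only to the next hospitalization (SAP 2.4.4.2). The IDMC reviews recurrence. This stands in full; what remains is that none of it can change the primary test or a planned check on it.

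**Loss from the denominator is an inference.** No sentence says that readmitted patients are missing. The data may be entered on case report forms not available here, Protocol 4.1 speaks of assessing status at the Day 29 call, and a readmitted patient may be read as still in hospital. This stands too: the loss is likely from the schedule, not certain.

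**The confirmatory tests are not reached by the second gap.** Readmitted patients remain primary events, and endpoints #1 and #2 are outside the hierarchy in SAP 2.4.4.3. Correct.

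**A first-event endpoint is a design choice.** Protocol 2.1 defends the 2-point change, and the fleeting-success example fits mainly baselines 2 and 3. From baseline 4, two points means score 6 or discharge, which a one-day change of oxygen device cannot produce. This limits the reach of the first gap and is a good reason to leave the primary analysis alone. It does not argue against a sensitivity analysis.

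**Counting every readmission as failure would also mislead.** A patient readmitted without oxygen (5) from baseline 4 is still one point better. If half of the readmitted in the 10%/4% example were still improved, the true difference would be 128/160 − 57.5/80 = 80.0% − 71.9% = 8.1 points. Dropping gives 10.6 (error 2.5) and a blanket failure rule gives 5.0 (error 3.1). Hence observed scores must come first.

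**Conclusion.** The point holds in two limited parts. The primary event carries no duration condition, and neither planned sensitivity analysis tests whether the result rests on transient improvement. The ordinal score of a readmitted patient is undefined, and on the scheduled data such patients would most likely leave endpoint #1, the daily 2-point proportions and the endpoint #2 model.

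The documents give no relapse or readmission rates, so the size can only be bracketed. With equal readmission of 2% to 10%, dropping these patients widens the planning difference by 0.5 to 2.8 points; in the smaller endpoint #1 example, 5% readmission widens it by 0.3. Larger distortion (5.8 points at 2%/10%, 5.6 in the 10%/4% example) needs readmission that differs between arms. A reader might infer that the response rates are biased in favour of sarilumab; nothing in the documents shows which arm, if either, would have more readmissions. The primary log-rank test and the stated power are not affected by the readmission rule.

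**What to change.** **1. Readmission score (SAP 2.4.4.1).** Reconcile the carry-forward sentence with the one on a second hospitalization. From the readmission date to the second discharge, use the recorded ordinal score; failing that, the oxygen-device score if device data exist. If neither exists, keep the patient in the denominator as not improved for the proportion endpoints. Use 7 again after the second discharge. Take readmission and discharge dates at the Day 29 call if they are not already captured.

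**2. One sensitivity analysis of the primary endpoint.** Date the event at the first day from which the patient stays at two or more points above baseline, or discharged, through Day 29 without dying. Status during a readmission follows rule 1. A patient who relapses and then recovers for good has the event at the later date. Patients with no such day are censored at Day 29. Rescue medication is handled as in the primary analysis.

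**Cost.** SAP wording, at most two date fields on a call that already asks about readmission, and one extra model. The sensitivity analysis will have fewer events and less power, so it should be read for consistency with the primary result. The primary analysis does not change. The latest version in SAP 1.6 (05-May-2020) predates Amended Protocol 04 (11-Jun-2020), and SAP 1.1 still describes 2:2:1 allocation, so a SAP update could carry both changes.
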